5.1.2. Analysis of Adverse Events

Number and percentage of participants with at least one particular AE (unsolicited/solicited) will be tabulated. Unsolicited AEs will be summarized by System Organ Class and Preferred Term. Solicited AEs will be summarized by class (local, systemic) and preferred term.

The following tables will be generated for solicited AEs: summary, by worst severity grade, at least Grade 3, related (systemic only), time to onset (in days) and duration (in days) for most frequent events and body temperature. Note that duration is defined as number of days from the start of the event until resolution of the event. The time to first onset is defined as (date of first onset – reference date + 1). The reference date is the start date of the vaccination period.

For unsolicited AEs, the following tables will be generated: summary table (including SAE, AE with fatal outcome, AEs leading to study discontinuation, and AEs leading to discontinuation of study vaccination), all events, most frequent, grade 3, permanent stop of vaccination, related and SAE.

Listings and/or participant narratives will be provided as appropriate, for those participants who die, discontinue study vaccinations due to an AE, or experience a severe or serious AE.

5.1.3. Phase allocation of Adverse Events

Solicited events are always allocated to the respective Post Dose period. Adverse events in the SDTM database are allocated to periods based on their start date/time. If the start date/time of an event falls between (or on) the start and stop date/time of a period, the AE is attributed to that period (treatment-emergent principle). A stepwise approach to allocate adverse events to the analysis periods/phases based on their start date/time is given in Attachment 2.

5.1.4. Missing Data

Missing data will not be imputed. Participants who do not report an event will be considered as participants without an event. An AE with a missing severity or relationship will be considered as an AE reported, but will be considered as not reported for the severity or relationship. For example, an AE with missing severity will be considered as an AE reported for the analysis of any grade, but will be considered as not reported for the analysis of grade 3.

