- f. MenACWY will be administered to all participants. After vaccination, participants will remain under observation at the study site for at least 30 minutes for presence of any acute reactions, or longer if deemed necessary by the investigator. Participant diaries will not be distributed. Infants that experience any symptoms will be invited to come for an unscheduled visit as needed.
- g. The brief physical examination (symptom-directed) includes also body length and weight. Physical examination findings (ie, abnormalities) prior to Dose 1 vaccination are to be recorded as medical history, after Dose 1 vaccination as adverse event.
- h. Prior to study intervention administration.

- i. Includes pulse/heart rate (at rest), respiratory rate, and body temperature.
- j. Prior to study intervention administration and at the end of the observation period.
- k. Diaries will be completed at home by either a project field worker who will visit the participant during daily visits or by the parent(s)/guardian to document symptoms of solicited local and systemic adverse events in the evening after each vaccination and then daily for the next 7 days at approximately the same time each day.
- 1. After the first and second vaccination, participants will remain under observation at the study site for at least 30 minutes for presence of any acute reactions, or longer if deemed necessary by the investigator. Solicited local and systemic and unsolicited adverse events emerging during the observation period will be recorded in the CRF.
- m. Solicited adverse events will be documented in the evening after the first and second vaccination and then daily for the next 7 days, during daily home visits by a project field worker.
- n. Serious adverse events and/or special reporting situations that are related to study procedures or that are related to non-investigational (concomitant) sponsor products will be reported from the time a signed and dated ICF is obtained onwards until the end of the study. All other serious adverse events and/or special reporting situations will be reported from the day of the first vaccination onwards until 6 months post-dose-2.
- o. Concomitant therapies must be recorded from screening onwards until 28 days post-dose-1 and from the second vaccination until 28 days post-dose-2. At the other time points, it should only be recorded if given in conjunction with serious adverse events.

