9.1.3. Vaccination Period

If eligible, the participant will come for the baseline visit (Day 1). The investigator should ensure that all enrollment criteria have been met during screening. If a participant's clinical status changes (including available laboratory results or receipt of additional medical records) after screening but before the first vaccination (Day 1) such that he/she no longer meets all enrollment criteria, then the participant should be excluded from further participation in the study.

Eligible participants will be allocated to an intervention arm as described in Section 5. Before each vaccination, a brief physical examination (including body length and weight) and measurement of vital signs will be performed.

Participants will be vaccinated as described in Section 6. After each vaccination, participants will remain under observation at the study site for at least 30 minutes for presence of any acute reactions, or longer if deemed necessary by the investigator. Following the first and second vaccination, any unsolicited, solicited local or systemic adverse events, and vital signs will be documented by study-site personnel at the end of this observation period.

Upon discharge from the site, parent(s)/guardian will be provided with a thermometer (to measure body temperature), a ruler (to measure local injection site reactions), and a participant diary to record body temperature and solicited local (at injection site) and systemic symptoms and will be trained on how to collect this information. Symptoms of solicited local and systemic adverse events will be collected in the diary in the evening after the first and second vaccination and then daily for the next 7 days at approximately the same time each day. Diaries will be completed at home by either a project field worker who will visit the participant during daily visits or by the parent(s)/guardian and checked by a project field worker. The investigator or clinical designee will review information from the participant's diary.

Participants will come to the site at 7 days after the first and second vaccination as indicated in the Time and Events Schedule. The participant's diary will be reviewed by study-site personnel. The investigator will examine the injection site for occurrences of erythema, swelling, or tenderness at these visits in order to complete the relevant parts of the CRF.

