2.1. Analysis Periods/Phases

Because the analysis of adverse events (AEs) will be presented per period (and not per time point), these will be assigned to the analysis periods based on Table 3 for the main study, and on Table 4 for the extension phase.

For the analysis that will be presented by time point (e.g. immunogenicity data), the electronic case report form (eCRF) visit schedules will be used for the post baseline assessments as follows:

- For the analysis based on the per protocol set, only assessments that fall within the protocol defined visit window will be used.
- For other analyses based on the full analysis set (if applicable), the assessments that fall outside the protocol defined windows will also be included. If only unscheduled visits are present for a time point, then the one closest to the scheduled visit will be used. If distances of multiple assessments to the scheduled visit are equal, the measurement with the latest date will be used.

		Interval			
Phase	Period	From	То		
Screening		Date and time of signing the informed consent form	One minute prior to start of post dose 1 period		
Regimen	Post-dose 1	Date and time of first vaccination	 Minimum of: a) 23:59 on the date of last contact (for early discontinuation) b) 23:59 on the date of database cut-off date in case of interim c) 23:59 of 28 days after the first vaccination (23:59 of day of vaccination + 28 days) d) One minute prior to post-dose 2 period 		
Follow-up 1		One minute after post-dose 1 period ends	 Minimum of: a) 23:59 on the date of last contact (for early discontinuation) b) 23:59 on the date of database cut-off date in case of interim c) One minute prior to post-dose 2 period 		
Regimen	Post-dose 2	Date and time of second vaccination	 Minimum of: a) 23:59 on the date of last contact (for early discontinuation) b) 23:59 on the date of database cut-off in case of interim analysis c) 23:59 of 28 days after the second vaccination (23:59 of day of vaccination + 28 days) 		
Follow-up 2		One minute after post-dose 2 period ends	 Minimum of: a) 23:59 on the date of last contact (for early discontinuation) b) 23:59 on the date of database cut-off in case of interim analysis c) 23:59 on the date of last study visit 		

Table 3: Analysis Period Definitions (Main Study)

		Interval		
Phase	Period	From	То	
eFollow-up 2		One minute after Follow-	One minute prior to signing the informed consent	
		up 2 phase ends	form	

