2.3.1. Full Analysis Set (FAS)

The full analysis set will include all participants with at least one study intervention administration documented.

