5. SAFETY

Safety analyses will be performed on the full analysis set. Continuous variables will be summarized using the following statistics, as appropriate: number of observations, arithmetic mean (mean), 95% CI for the mean, standard deviation (SD), standard error (SE), median, quartiles (Q1 and Q3), minimum and maximum. Frequencies and percentages (one decimal place) will be generated for categorical variables. No formal comparisons between groups will be provided.

The safety data will be presented by vaccine regimens (ie, intervention arms) as described in the study protocol. The data will be presented by analysis period (post-dose 1 and post-dose 2) as well as over the entire regimen period (ie, combined post-dose 1 and post-dose 2 periods). Denominator for the percentages will be the number of participants in the considered population and period/phase for a certain regimen (eg, incidence per 100 participants/period).

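### SAP 5.1.4 scores a vaccinated infant with no solicited data after the clinic observation as reaction-free, which lowers the tabulated 7-day percentage or leaves it unchanged relative to complete ascertainment

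*SAP*

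**What the plan says.** Four provisions of the SAP combine.

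- Population (SAP 2.3.1): "The full analysis set will include all participants with at least one study intervention administration documented". There is no condition on available data, and SAP 5 runs all safety analyses on this set.
- Denominator (SAP 5): "Denominator for the percentages will be the number of participants in the considered population and period/phase for a certain regimen".
- Missing data (SAP 5.1.4): "Missing data will not be imputed. Participants who do not report an event will be considered as participants without an event". Solicited events are not excepted.
- Tables (SAP 5.1.2): "Solicited AEs will be summarized by class (local, systemic) and preferred term". SAP 5.1.1 takes the tabulated solicited events from the investigator assessment pages of the eCRF.

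The protocol sets the collection. The observation footnote of the Time and Events Schedule says: "Solicited local and systemic and unsolicited adverse events emerging during the observation period will be recorded in the CRF". Footnote m says: "Solicited adverse events will be documented in the evening after the first and second vaccination and then daily for the next 7 days". Footnote k lets either a field worker or a parent complete the diary. At the 7-day visits staff review the diary, and Protocol 9.1.3 adds: "The investigator will examine the injection site for occurrences of erythema, swelling, or tenderness at these visits". The Schedule also lists a brief symptom-directed physical examination on Day 8 and Day 64.

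In SAP 2.1, Table 3, the post-dose 2 period opens at "Date and time of second vaccination", so an infant who never receives Dose 2 is not in that denominator. Early loss shortens a period but does not remove the infant from it.

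**The concern.** Unsolicited events are volunteered, so treating silence as no event is a reasonable convention. Solicited events are asked about by name every day, and a blank record then means that nobody looked. SAP 5.1.4 says that nothing is imputed, yet its next sentence in effect assigns no event to the unobserved infant.

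The study is descriptive, so the percentage and its denominator are the result. As planned, the tables do not let a reader separate an infant who was observed without a reaction from one who was not observed. SAP 4.2 gives discontinuations and numbers per period, which is not the same as numbers with solicited data. The secondary immunogenicity endpoint gets more care: SAP 2.3.2 restricts the analysis to participants with available data and repeats it on the full analysis set if more than 10% are excluded.

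**Working it through.** **Inputs.** Planned arm sizes are 73 and 34 (Protocol 11.2). The illustrative rate is 44.3% for any solicited event, 85 of 192 children aged 1-3 years (Protocol 1.1, Table 1). Those are blinded data from another study, not per-dose rates in infants. The number of unobserved infants, m, is not in the documents and is assumed throughout.

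**1. The plan's own figures.** Protocol 11.2 states that zero reactions give 95% confidence of a true rate below 4.0% (N = 73) or 8.4% (N = 34). The one-sided exact bound 1 − 0.05^(1/N) gives 4.02% and 8.43%, so both figures reproduce. They assume that every infant is observed. With N − m observed:

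| m | N = 73 | N = 34 |
|---|---|---|
| 0 | 4.02% | 8.43% |
| 2 | 4.13% | 8.94% |
| 4 | 4.25% | 9.50% |
| 7 | 4.44% | 10.50% |

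**2. Direction.** Let x be the number of observed infants with an event. Among the m infants without later data, let c have a clinic-recorded event and h an unseen one. The table shows (x + c)/N. Complete ascertainment would show (x + c + h)/N. Since h ≥ 0, the tabulated value is never higher, and the two are equal when h = 0. Enumeration over N = 73 and 34 with m from 0 to 10 found no exception.

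**3. Size when missingness is unrelated to events and c = 0.** Shift = rate × m/N.

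- N = 73: 44.3 × 1/73 = 0.6 points; 44.3 × 2/73 = 1.2 points.
- N = 34: 44.3 × 1/34 = 1.3 points; 44.3 × 2/34 = 2.6 points.

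**4. A deliberately high case, m = 7 of 73 with x = 29 and c = 0.** Tabulated: 29/73 = 39.7% (exact 95% CI 28.5 to 51.9). Among observed infants: 29/66 = 43.9% (31.7 to 56.7). If all 7 had reacted: 36/73 = 49.3%. The 4.2-point gap between the first two is well inside a CI half-width of about 12 points.

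**5. When does an available-data rate do better?** Let f = m/N, p the rate among observed infants and q the rate among unobserved infants. The full-cohort rate is (1 − f)p + fq. With c = 0, the planned rule errs by −fq and the available-data rate by f(p − q). The second is smaller in size whenever q > p/2, for any f > 0. With p = 44.3% the threshold is 22.15%. For f = 2/73:

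| q | Planned rule | Available data |
|---|---|---|
| 15% | −0.41 points | +0.80 points |
| 30% | −0.82 points | +0.39 points |
| 60% | −1.64 points | −0.43 points |

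**The case against.** The strongest case against is that the affected group may be close to empty. To belong to it, an infant must miss every daily home recording and also the 7-day visit. Nothing is tested, no formal group comparison is planned, and every value of m above is assumed. Missed visits also leave some trace: SAP 4.4 summarises and lists major deviations, and the protocol's COVID-19 appendix has missed assessments captured. This stands as to size. It does not supply the missing count, since none of these outputs says how many infants had solicited data. The same appendix expects some visits to be remote or delayed.

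A second objection is that an available-data rate is not uniformly better. That also stands: step 5 shows the planned rule is closer when unobserved infants react at less than half the observed rate. Dropping an infant seen to react at the clinic and then lost would also discard a real event. Both are reasons to keep the planned table and add to it.

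Three stronger readings are tempting, and the documents do not support them.

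- A reader might infer that the 7-day visit looks only at the injection site, leaving systemic events unassessed there. The Schedule also lists a symptom-directed examination at those visits, alongside the diary review.
- A reader might infer that missed second doses dilute the post-dose 2 rate. Table 3 of the SAP excludes those infants from that period.
- A reader might infer that the planned rule gives the lower figure against any alternative. It does so against complete ascertainment. Against simply dropping an infant who had a clinic event it can be higher: 11/73 = 15.1% against 10/72 = 13.9%.

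**Conclusion.** The point holds as a small, one-directional weakness in how a primary endpoint is tabulated. SAP 5.1.4, the full analysis set and the period denominator together score an unobserved infant as reaction-free, and no other section corrects this. The effect is zero with complete data. It is about 0.6 to 1.2 points in the vaccine arm, or 1.3 to 2.6 in the control arm, for one or two unobserved infants at an illustrative 44.3%.

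Those sizes rest on an assumed number missing, a rate borrowed from older children, and missingness unrelated to reactions. A clinic event is protected only if it is entered on the investigator assessment pages, because those feed the tables. The documents do not support calling the bias material or saying that it would change a conclusion. This is an improvement to consider.

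**What to change.** For solicited events only:

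1. Report by arm and dose the number of infants with solicited data after the clinic observation (diary or investigator assessment page) and the number of diary days completed. Diary days matter because an infant with one recorded day counts as having data while the blank days are still scored event-free.
2. In the solicited summary table, beside the planned percentage, give the percentage among infants with solicited data for that dose. Use one denominator per dose for local, systemic and any solicited event. For the combined regimen period, use infants with data after at least one dose received. Define availability from the same source as the numerator, which SAP 5.1.1 makes the investigator assessment pages, and independently of whether an event occurred.
3. Keep the planned all-vaccinated table, so that events seen only at the clinic still count.

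Leave the unsolicited and serious adverse event rules as they are.

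The cost is a few sentences in the SAP, one availability flag per dose, some completeness rows and one extra column in the summary table, repeated across its period and age-group displays. Denominators will differ slightly between solicited and unsolicited tables and need a footnote. The added rate should not be presented as the correct one: it is closer to the full-cohort rate only when unobserved infants react at more than half the observed rate, which is why both belong in the table.

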5.2. Laboratory, Vital Signs and Physical Examinations

Laboratory abnormalities will be determined according to the toxicity grading tables (see Attachment 1), and in accordance with the normal ranges of the clinical laboratory. Laboratory and vital signs abnormalities/toxicities will not be summarized since assessments are only done at screening and pre-dose 2. Clinically significant abnormal laboratory data reported in the CRF will be presented in the data listings.

A full physical examination is only conducted at screening. At other visits, only abbreviated, symptom-directed examinations are performed per the investigator's discretion and the clinically significant abnormal findings are recorded as AEs. Therefore, separate analysis of physical examination findings will not be performed.

6. IMMUNOGENICITY ANALYSIS

6.1. Parameters

Humoral immune responses as measured by the following assays will be analyzed:

- Binding antibody responses using Filovirus Animal Nonclinical Group (FANG) ELISA: Quantification of antibodies binding to EBOV GP using the EU/mL readout.
- Neutralizing antibody response against the adenovirus backbone (Ad26 VNA)

6.2. Handling of Missing and/or Unquantifiable Immune Response Data

For both ELISA binding antibody responses (EU/mL) and Ad26 VNA (IC₉₀ Titer), values below the respective lower limit of quantification (LLOQ) will be imputed with half of the corresponding LLOQ (ie, LLOQ/2) and values above the upper limit of quantification (ULOQ) will be imputed with the ULOQ. For the calculation of fold changes (if applicable), the values below LLOQ will be imputed with the corresponding LLOQ and values above the ULOQ will be imputed with the ULOQ.

6.3. Immune Response Analysis

No formal hypothesis on immunogenicity will be tested.

6.3.1. Immunogenicity Against the Insert:

6.3.1.1. Humoral Assays

The following will be defined for binding antibody responses as measured by EBOV GP Filovirus Animal Nonclinical Group (FANG) ELISA (EU/mL):

- **Sample interpretation:** A sample will be considered positive, if the value is above the LLOQ.
- **Responder:**
 - If sample interpretation is negative at baseline but positive post-baseline and the post-baseline value is greater than 2.5×LLOQ; OR
 - If sample interpretation is positive at both baseline and post-baseline and there is a greater than 2.5-fold increase from baseline (2.5-fold increase on the original scale).

The analysis of binding antibody responses (EU/mL) will be presented by age category per intervention arm. The following outputs will be generated:

- Table of summary statistics (ie, geometric means and corresponding 95% CIs, geometric mean fold increase [from Pre-dose 1] with corresponding 95% CI), responder rates and positive sample interpretation (ie, showing number, percentage and the exact 95% Clopper-Pearson CI).
- Table of summary statistics (ie, geometric means and corresponding 95% CIs, geometric mean fold increase [from Pre-dose 1] with corresponding 95% CI), responder rates and positive sample interpretation (ie, showing number, percentage and the exact 95% Clopper-Pearson CI) by pre-existing antibody response against Ad26 vector (ie, pre-existing Ad26 versus no pre-existing Ad26).
- Graphic (on a log₁₀-scale) of regimen profiles of the geometric mean concentrations with 95% CIs.
- Graphic (on a log₁₀-scale) of regimen profiles of the geometric mean concentrations with 95% CIs by pre-existing antibody response against Ad26 vector (ie, pre-existing Ad26 versus no pre-existing Ad26).
- Dot plots (on a log₁₀-scale) with distinction between positive and negative sample interpretations.
- Data listing.

6.3.2. Immunogenicity Against the Vector

For the analysis of the immunogenicity against Ad26 vector (backbone), a sample value will be considered positive if it is above the assay LLOQ. The data will be presented as follows:

- Table of summary statistics (geometric means and its corresponding 95% CIs) and positive sample interpretation (ie, showing number, percentage and the exact 95% Clopper-Pearson CI).
- Dot plots (on a log₁₀-scale) with distinction between positive and negative sample interpretations
- Scatter plot (on a log₁₀-scale) with Spearman's correlation coefficient of 21 days postdose 2 binding antibody responses (EU/mL) against baseline Ad26 vector neutralization antibodies.
- A data listing

REFERENCES

- VAC52150EBL2005 Protocol Amendment 3: A Phase 2 Study to Evaluate the Safety, Reactogenicity, and Immunogenicity of a Heterologous 2-dose Vaccination Regimen Using Ad26.ZEBOV and MVA-BN®-Filo in Infants Aged 4-11 Months in Guinea and Sierra Leone. London School of Hygiene and Tropical Medicine, Institut National de la Santé et de la Recherche Médicale, University of Antwerp, College of Medicine and Allied Health Sciences, and Janssen Vaccines & Prevention B.V. (1 October 2019).
- VAC52150EBL2005 Independent Data Monitoring Committee Charter. Janssen Vaccines & Prevention B.V. (July 2019)
- 3. VAC52150EBL2005 Independent Data Monitoring Committee Statistical Analysis Plan. Janssen Vaccines & Prevention B.V. (July 2019)
- 4. WHO Child Growth Standards (birth to 24 months). Available at: https://www.who.int/childgrowth/standards/weight_for_age/en/. Accessed April 2019.
- 5. VAC52150EBL2005 Protocol Amendment 3: A Phase 2 Study to Evaluate the Safety, Reactogenicity, and Immunogenicity of a Heterologous 2-dose Vaccination Regimen Using Ad26.ZEBOV and MVA-BN®-Filo in Infants Aged 4-11 Months in Guinea and Sierra Leone. London School of Hygiene and Tropical Medicine, Institut National de la Santé et de la Recherche Médicale, University of Antwerp, College of Medicine and Allied Health Sciences, and Janssen Vaccines & Prevention B.V. (28 September 2021).

ATTACHMENTS

1. TOXICITY GRADING SCALE FOR HEALTHY PEDIATRIC PARTICIPANTS UP TO 3 YEARS OF AGE ENROLLED IN PREVENTIVE VACCINE CLINICAL TRIALS

Adapted from: Division of Microbiology and Infectious Diseases (DMID Pediatric Toxicity Tables (November 2007, draft). For adverse events not included in the tables below, refer to the severity criteria guidelines in Section 12.1.3 of the CTP. Local lab references take preference over the DMD table and the different grades. The abbreviations used in the following tables are: LLN: lower limit of normal; IV: intravenous; ULN: upper limit of normal.

	Grade 1	Grade 2	Grade 3	Grade 4
Tenderness	Mild discomfort to touch; minimal to no limitation of use of limb	Notable discomfort to touch; Greater than minimal limitation of use of limb	Significant discomfort at rest; Severe limitation of use of limb	Hospitalization or ER visit for treatment
Erythema	<10 mm	10-25 mm	26-50 mm	>50 mm or any grade 3 with hospitalization or ER visit for treatment
Swelling	<10 mm	10-25 mm	26-50 mm	>50mm or any grade 3 with hospitalization or ER visit for treatment
HEMATOLOGY				
	Grade 1	Grade 2	Grade 3	Grade 4
Hemoglobin for children greater than 3 months and less than 2 years of age	9.0-9.9 gm/dL	7.0-8.9 gm/dL	<7.0 gm/dL	Cardiac Failure secondary to Anemia
Hemoglobin for children greater than 2 years of age	10.0-10.9 gm/dL	7.0-9.9 gm/dL	<7.0 gm/dL	Cardiac Failure secondary to Anemia
Absolute Neutrophil Count	750-1200/mm ³	400-749/mm ³	250-399/mm ³	<250/mm ³
Platelets	75,000-99,999/mm ³	50,000-74,999/mm ³	25,000-49,999/mm ³	<25,000/mm ³
Prothrombin Time (PT)	1.1-1.2 x ULN	1.3-1.5 x ULN	1.6-3.0 x ULN	>3.0 x ULN
Partial Thromboplastin Time (PTT)	1.1-1.6 x ULN	1.7-2.3 x ULN	2.4-3.0 x ULN	>3.0 x ULN
GASTROINTESTINAL				
	Grade 1	Grade 2	Grade 3	Grade 4
Bilirubin (Fractionated b	ilirubin test must b	e performed when	total bilirubin is ele	vated)
Bilirubin for children greater than 3 months of age (when accompanied by any increase in other liver function test)	1.1- <1.25 x ULN	1.25- <1.5 x ULN	1.5-1.75 x ULN	>1.75 x ULN
Bilirubin for children greater than 3 months of age (when	1.1- <1.5 x ULN	1.5- <2.0 x ULN	2.0-3.0 x ULN	>3.0 x ULN

CONFIDENTIAL – FOIA Exemptions Apply in U.S.

		5	latistical Analysis I la	I VIICO2100EDE200
other liver functions are in the normal range)				
AST (SGOT)	1.1- <2.0 x ULN	2.0- <3.0 x ULN	3.0-8.0 x ULN	>8.0 x ULN
ALT (SGPT)	1.1- <2.0 x ULN	2.0- <3.0 x ULN	3.0-8.0 x ULN	>8.0 x ULN
GGT	1.1- <2.0 x ULN	2.0- <3.0 x ULN	3.0-8.0 x ULN	>8.0 x ULN
Pancreatic Amylase	1.1- 1.4 x ULN	1.5- 1.9 x ULN	2.0-3.0 x ULN	>3.0 x ULN
Uric Acid	7.5-9.9 mg/dL	10.0-12.4 mg/dL	12.5-15.0 mg/dL	>15.0 mg/dL
Loss of Appetite	Feeding minimally reduced	Feeding reduced by more than 50% of normal for the child	Refusing all feeds	No solid or liquid taken orally for in the last 24 hours; requires intravenous fluids
Diarrhea	Change in consistency of stools OR increase of 1-3 stools over baseline per 24-hour period	liquid/watery stools OR increase of 4 to 6 stools over baseline per 24-hour period	Increase of ≥7 stools over baseline per 24-hour period	Requires IV fluid resuscitation and electrolytes repletion OR hypotensive shock
Constipation	Slight change in consistency and/or frequency of stools	Hard, dry stools with a change in frequency	Intestinal obstruction accompanied with abdominal pain	Hospitalization; Severe abdominal distention and vomiting accompani ed with severe abdominal pain
Vomiting	1 episode/ day (24h)	2-3 episodes per day (24h)	4-6 episodes per day (24h)	Greater than 6 episodes per day (24h) OR intractable vomiting
ELECTROLYTES				
	Grade 1	Grade 2	Grade 3	Grade 4
Creatinine		1		1
	0.0.0	0.0.1.1	1215	5.1 E LU N
3 Months – 2 Years of age	0.6-0.8 x ULN	0.9-1.1 x ULN	1.2-1.5 x ULN	> 1.5 x ULN
2 Years – 3 Years of age	0.7-1.0 x ULN	1.1-1.6 x ULN	1.7-2.0 x ULN	>2.0 x ULN
Hypernatremia		145-149 mEq/L	150-155 mEq/L	>155 mEq/L or abnormal sodium AND mental status changes
Hyponatremia		130-135 mEq/L	129-124 mEq/L	<124 mEq/L or abnormal sodium AND mental status changes
Hyperkalemia	5.0-5.9 mEq/L	6.0-6.4 mEq/L	6.5-7.0 mEq/L	>7.0 mEq/L or abnormal potassium AND cardiac arrhythmia
Hypokalemia	3.0-3.5 mEq/L	2.5-2.9 mEq/L	2.0-2.4 mEq/L	<2.0 mEq/L or abnormal potassium AND cardiac arrhythmia
Hypercalcemia	10.5-11.2 mg/dL	11.3-11.9 mg/dL	12.0-12.9 mg/dL	>13.0 mg/dL
Hypocalcemia	7.8-8.4 mg/dL	7.0-7.7 mg/dL	6.0-6.9 mg/dL	>6.0 mg/dL
Hypomagnesemia	1.2-1.4 mEq/L	0.9-1.1 mEq/L	0.6-0.8 mEq/L	<0.6 mEq/L or

CONFIDENTIAL – FOIA Exemptions Apply in U.S.

Statistical Analysis Plan VAC52150EBL2005

			-	I VAC52150EBE200
hypoglycemia	55-65 mg/dL	40-54 mg/dL	30-39 mg/dL	<30 mg/dL or adnormal glucose AND mental status changes
Hyperglycemia	116-159 mg/dL	160-249 mg/dL	250-400 mg/dL	>400 mg/dL or ketoacidosis
Proteinuria	Tr-1+ or <150 mg/day	2+ or 150-499 mg/day	3+ or 500-1000 mg/day	4+ or Nephrotic syndrome >1000 mg/day
Hematuria	Microscopic <25 cells/hpf	Microscopic >25 cells/hpf	Gross hematuria	Hospitalization; Life threatening consequences
Neurologic				
	Grade 1	Grade 2	Grade 3	Grade 4
Irritability	Easily consolable; minimal or no interference with activity. Episodes of continuous crying <60 min.	Difficult to console. Episodes of continuous crying >60 min <120 min	Inconsolable, prevents daily activity. Episodes of continuous crying >120 min	Hospitalization or EF visit for treatment
Decreased Activity	Minimal decrease in alertness, minimal or no interference with activity	Some interference with activity, slightly subdued	unable to achieve normal level of alertness, lethargic	ER visit or hospitalization for treatment or life- threatening consequences
Neuropathy/ Lower Motor Neuropathy		Mild transient Paresthesia only	Persistent or progressive paresthesia, burning sensation in feet, or mild dysesthesia; no weakness; mild to moderate deep tendon reflex changes; no sensory loss	Onset of significant weakness, decrease or loss of DTRs, sensory loss in "stocking glove" distribution, radicular sensory loss, multiple crania nerve involvement; bladder or bowel dysfunction, fasciculations, respiratory embarrassment from chest wall weakness.
Myopathy or Neuromuscular Junction Impairment	Normal or mild (<2 x ULN) CPK elevation	Mild proximal weakness and/or atrophy not affecting gross motor function. Mild myalgias, +/- mild CPK elevation (<2 x ULN)	Proximal muscle weakness and/or atrophy affecting motor function +/- CPK elevation; or severe myalgias with CPK >2 x ULN;	Onset of myasthenia-like symptoms (fatigable weakness with external, variable ophthalmoplegia and/or ptosis), or neuromuscular junction blockade (acute paralysis) symptoms
OTHER	1	1	1	, , ,
	Grade 1	Grade 2	Grade 3	Grade 4

Statistical Analysis Plan VAC52150EBL2005

Acute allergic reaction	Pruritus without Rash	Pruritic Rash	Mild Urticaria	Severe Urticaria Anaphylaxis, Angioedema
Stomatitis	Mild discomfort	Painful, difficulty swallowing, but able to eat and drink	Painful: unable to swallow solids	Painful: unable to swallow liquids; requires IV fluids
Illness or clinical adverse event (as defined according to applicable regulations)	No interference with activity	Some interference with activity not requiring medical intervention	Prevents daily activity and requires medical intervention	Hospitalization

